## **9 SAFETY AND REPORTABLE EVENTS**

Bupirone is FDA-approved for the treatment of generalized anxiety disorder with a well-established side effect profile, with common adverse events (>5%) including dizziness, drowsiness, nausea, and headache. Package insert information for bupirone can be found at [http://www.accessdata.fda.gov/drugsatfda\\_docs/nda/2000/21-190\\_BuSpar\\_Prntlbl.pdf](http://www.accessdata.fda.gov/drugsatfda_docs/nda/2000/21-190_BuSpar_Prntlbl.pdf) and is also included in RSRB application section 50.1. There is some data to suggest that bupirone may cause worsening of PD motor function and this will be monitored with the use of the MDS-UPDRS motor scale. Hypertensive crisis has been reported and concomitant MAOI use will be prohibited. There have been case reports of possible serotonin syndrome in patients receiving bupirone and fluoxetine, sertraline, citalopram, and fluvoxamine. However, bupirone is commonly co-prescribed with SSRIs and in a study examining bupropion versus bupirone for augmentation of citalopram for treatment of depression, 286 participants were randomized to the bupirone-citalopram arm and there were no reports of serotonin syndrome. All

participants will be monitored closely. Safety and tolerability will be closely monitored by study investigators. If an intolerability or adverse event occurs, depending on the severity of the event, investigators will decide whether to decrease study drug dosage or to discontinue the study drug. Participants will be able to withdraw from the study at any time.

### 9.1 Adverse Event Definition

An adverse event is any symptom, sign, illness, or event which develops or worsens during the course of the study, whether or not the event is considered related to study drug.

### 9.2 Serious Adverse Event

A serious adverse event is defined as any adverse medical event that results in any of the following outcomes:

- death;
- is life-threatening;
- requires inpatient hospitalization or prolongation of existing hospitalization;
- results in persistent or significant disability/incapacity;
- is a congenital anomaly/birth defect; or
- requires medical or surgical intervention to prevent permanent impairment or damage.

In addition any event which the investigator regards as serious or which would suggest any significant hazard, contraindication, side effect or precaution that may be associated with the use of the drug should be reported as a serious adverse event

### 9.3 Recording Adverse Events

At each participant visit the site study staff will assess adverse events by recording all voluntary complaints of the participant and by assessment of clinical features. At each study visit, the participant should be questioned directly regarding the occurrence of any adverse events since his/her last visit. Soliciting of adverse events should be non-specific and participants should be asked the question, "Do you feel different in any way since starting the new treatment?"

All adverse events, whether observed by an investigator, elicited from or volunteered by the participant, should be documented on an Adverse Event CRF. Each adverse event will include a brief description of the experience, the date of onset, the date of resolution, the duration and type of experience, the severity, the relationship to investigational product (i.e., drug or device), contributing factors, and any action taken with respect to the study drug/device. This should also include the investigator's opinion of the possible relationship between the adverse event and the study drug or participation in the study. Likely alternative etiologies should be recorded for events considered unrelated to study drug.

Adverse events already documented at a previous visit and designated as 'continuing' should be reviewed at each visit. The investigator is obliged to follow participants with

adverse events until the event has resolved, the condition is considered medically stable, or the participant is no longer available for follow up. Participants who discontinue the study drug due to adverse events will be treated and followed according to established acceptable medical practice. A follow up telephone call will be made to all participants who have unresolved adverse events 30 days from the date of the final study visit. If an adverse event is resolved, the documentation in the CRF must be completed to that effect. If an adverse event changes in frequency or severity during a study period, a NEW record of that event will be initiated. A record of all adverse events will be reviewed periodically by the study investigators.

The recording of adverse events will begin to occur once the participant signs informed consent and continue until the participant completes the study or withdraws from participation.

#### 9.4 Responsibilities for Reporting Serious Adverse Events

The investigator should record all serious adverse events that occur during the study period on an Adverse Event CRF. Details included will be the same as those documented for adverse events (as detailed above). The investigator or their designee will fill out the MedWatch FDA 3500 form for serious adverse events. This will include: an identification that serious event criteria have been met; a detailed description of the event and other relevant information; the current status of the event; if the subject has died, the date of death and autopsy report, if available; and the investigator's current opinion of the relationship between the event and the study drug/participation in the study.

The recording of adverse events will begin to occur once the participant signs informed consent and continue until the participant completes the study or withdraws from participation.

The investigator will comply with regulations and RSRB policy regarding the reporting of adverse events.

#### 9.5 Assessment of Severity

Clinical adverse events will be graded on a three-point scale (mild, moderate, severe) and reported on the CRF and in the log. The definitions are as follows:

MILD	no limitation of usual activities
MODERATE	some limitation of usual activities
SEVERE	inability to carry out usual activities

#### 9.6 Assessment of Relationship

For each adverse event, the relationship to the study drug will be coded as follows:

DEFINITE	Causal relationship is certain (i.e., the temporal relationship between drug exposure and the adverse event onset/course is reasonable, there is a clinically compatible response to de-challenge, other causes have been
----------	---

eliminated and the event must be definitive pharmacologically or phenomenologically using a satisfactory re-challenge procedure, if necessary).

**PROBABLE** High degree of certainty for causal relationship (i.e., the temporal relationship between drug exposure and the adverse event onset/course is reasonable, there is a clinically compatible response to de-challenge [re-challenge is not required] and other causes have been eliminated or are unlikely).

**POSSIBLE** Causal relationship is uncertain (i.e., the temporal relationship between drug exposure and the adverse event onset/course is reasonable or unknown, de-challenge/re-challenge information is either unknown or equivocal and while other potential causes may or may not exist, a causal relationship to the study drug does not appear probable).

**UNLIKELY** Not reasonably related, although a causal relationship cannot be ruled out (i.e., while the temporal relationship between drug exposure and the adverse event onset/course does not preclude causality, there is a clear alternate cause that is more likely to have caused the adverse event than the study drug).

**UNRELATED** No possible relationship (i.e., the temporal relationship between drug exposure and the adverse event onset/course is unreasonable or incompatible, or a causal relationship to study drug is implausible).

## 10 RISK/BENEFIT ASSESSMENT

### 10.1 Potential Risks

Potential risks of participating in the study include side effects of therapy. The most common side effects of buspirone include dizziness, drowsiness, headaches, nausea, and nervousness. 10% of those who participated in premarketing clinical efficacy trials for BuSpar stopped treatment as a result of an adverse event (label). In placebo-controlled clinical trials the most common adverse events were: dizziness (12%), drowsiness (10%), nausea (8%), headache (6%), nervousness (5%), fatigue (4%), insomnia (3%), lightheadedness (3%), dry mouth (3%), weakness (2%), numbness (2%), abdominal/gastric distress (2%), diarrhea (2%), blurred vision (2%), depression (2%), confusion (2%), anger/hostility (2%), excitement (2%), and decreased concentration (2%) (label). Some studies have shown worsening of PD motor function with buspirone treatment. However, in the two largest studies this occurred only with dosages higher than 60 mg/day, which will not be used in this study, and it is only in a small (n=5) open-label study where worsening of PD motor function was reported with lower dosages. There are case reports of possible serotonin syndrome occurring with concomitant SSRI use, however, in clinical practice buspirone and SSRIs are commonly co-prescribed. All participants will be monitored closely. The participant's anxiety may not improve or may worsen during the course of the study. Participants will be encouraged to contact the investigators at any time if there is concern about worsening anxiety or adverse events.

Participants will also be forgoing the initiation of other potential treatment options, including medications and non-pharmacological therapy, for the duration of the trial. Although there is currently insufficient evidence to guide the choice of therapy in the treatment of anxiety in Parkinson's disease, there is evidence to support the use of a variety of different anxiolytics as well as non-pharmacological therapy options in the general population, and these are often offered as treatment options in clinical practice. Participants may experience a lack of improvement or worsening of anxiety during the trial.

Participants may find it uncomfortable to respond to some of the questions contained in the evaluations. Participants will not be required to answer any questions that make them uncomfortable. Breach of confidentiality is a potential risk. If a breach of confidentiality occurs, the participant(s) will be immediately notified and appropriate steps will be taken to minimize the risk of a future breach of confidentiality occurring.

## 10.2 Protection Against Risks

To minimize the risk of side effects, we will follow the recommended titration schedule for buspirone. Safety and tolerability will be closely monitored by study investigators. If an intolerability or adverse event occurs, depending on the severity of the event, investigators may decide to decrease the study drug/placebo dosage or to discontinue the study drug/placebo. Participants will be able to withdraw from the study at any time.

Participants in either the study drug or placebo arm may experience worsening of their anxiety. If a participant develops suicidal ideation, which is deemed severe enough by an investigator to reflect a significant suicidal risk, we will terminate the participant from the study and we will immediately refer the patient to a mental health provider for treatment. The investigator will determine the most appropriate referral, which may be referral to an outpatient mental health provider or referral to the Comprehensive Psychiatric Emergency Program. Participants and their caregivers will be encouraged to contact the investigators at any time if there is concern about worsening anxiety. As detailed in section 5.1, investigators will re-evaluate the dosage every two weeks and make dosage adjustments as necessary and tolerated up to a maximum of 30 mg twice daily to achieve an optimal dosage that balances efficacy with tolerability. If, in the opinion of either the participant or the investigator, the level of anxiety is resulting in a degree of emotional distress or impairment considered to be unacceptable, the participant's participation in the study will be terminated and the subject will be referred immediately to a mental health provider for treatment.

Un-blinding of treatment assignment can occur if it is medically required to reveal a participant's actual treatment. This should only occur in consultation with the principal investigator unless there is a medical emergency and the principal investigator cannot be immediately reached. There are very few reasons (eg. medication overdose) that medically require such un-blinding and worsening of baseline anxiety would not in and of itself be considered sufficient cause for un-blinding.

To minimize the risks of breach of confidentiality, study data will be collected using the University of Rochester's REDCap (Research Electronic Data Capture) system, designed specifically for use in research, which restricts access to study data.

REDCap servers are housed in a local data center at the University of Rochester and all web-based information transmission is encrypted. REDCap was developed in a manner consistent with HIPAA security requirements and is recommended to University of Rochester researchers by the URM Research Privacy Officer and Office for Human Subject Protection. All study documents will be reviewed for consistency and completeness when entered into the REDCap database. Each eligible participant will be assigned a unique subject identifier. Data will be collected in a de-identified manner. The log linking subject identifiers to identifying participant information will be destroyed once study data have been fully verified by study investigators. Any paper documents will be stored in locked filing cabinets. The screening log will be destroyed once study recruitment has been completed and study data have been fully verified by study investigators.

All study personnel will be appropriately trained in the administration of study assessments.

### **10.3 Potential Benefits to Subjects**

Participants may experience an improvement in anxiety as a result of participation in this study, however, buspirone is readily available and may be prescribed in the context of routine clinical care.

### **10.4 Alternatives to Participation**

Patients who decline to participate in the study will receive routine clinical care.

## **11 CONFIDENTIALITY OF DATA AND INFORMATION STORAGE**

Each participant will be assigned a unique subject identifier. Study data will be collected using the University of Rochester's REDCap system, designed specifically for use in research, which restricts access to study data to individuals granted access. All records pertaining to the study will be kept in a secure location with limited access and destroyed according to institutional guidelines.

Clinical information will not be released without written permission of the participant, except as necessary for monitoring by the IRB, OHSP, the sponsor, or the sponsor's designees. An intentional breach of confidentiality may occur if the investigator feels that the participant represents a risk to him or herself or others as is standard medical practice.

## **12 RESEARCH INFORMATION IN MEDICAL RECORDS**

Information concerning participation in this study will be included in the participant's medical record.

## **13 DATA ANALYSIS AND MONITORING**

### **13.1 Sample Size Determination**

The primary outcome for tolerability is the proportion of participants who fail to complete the 12-week study on study drug (intolerability). This study uses a single-

arm futility design to determine the tolerability of buspirone by comparing the observed intolerability rate ( $\theta_E$ ) against an intolerability rate that would be unacceptably high ( $\theta_O$ ). 20% represents a reasonable value for unacceptably high intolerability ( $\theta_O$ ). Our null hypothesis is that buspirone is tolerable and  $\theta_E \leq \theta_O$ . Our alternative hypothesis is that buspirone is intolerable and that  $\theta_E > \theta_O$ . A sample size of 21 will provide 80% power to reject the null hypothesis of tolerability (observed intolerability  $\leq 20\%$ ) in favor of the alternative hypothesis of intolerability (observed intolerability  $> 20\%$ ) if the true intolerability is greater than 40%, using a binomial test and a one-tailed significance level of 10% significance. With the introduction of a placebo arm for blinding and relying on a 4:1 allocation ratio, the desired sample size increases to 27. We are willing to accept a higher chance that we declare an intolerable drug tolerable as the expected intolerabilities (headache, nausea, drowsiness, dizziness, and temporary worsening of PD motor function) are not expected to be serious and could be confirmed in larger studies. We are more concerned about declaring a truly tolerable drug intolerable and not moving forward with larger studies.

### 13.2 Planned Statistical Analysis

The primary outcome for tolerability is the proportion of participants who fail to complete the 12-week study on study drug, as described in **Sample Size and Accrual**. The number of participants who fail to complete the study on study drug will be determined and if 7 or more participants fail to tolerate the study drug, the null hypothesis will be rejected. Participants who do not complete the study on study drug for any reason will be considered as experiencing intolerability for purposes of the primary analysis.

As a secondary analysis we will calculate the number of participants who fail to complete the study on study drug due to adverse events; separating them from those who fail to complete the study on study drug for alternative reasons. We will also calculate the number of participants who required dosage reductions during the study and use descriptive statistics to describe the average study drug dosage and dosage reductions.

Safety analyses will include tabulating adverse events by treatment group and severity and codifying the relationship to study drug. Serious adverse events attributable to buspirone treatment will be described in detail. Adverse event incidence will be summarized along with the corresponding 95% two-sided confidence interval. The mean change in MDS-UPDRS motor score and from baseline to 12 weeks will be calculated. We will use descriptive statistics to characterize the range and variability of study drug dosages.

Secondary outcomes related to anxiety will include the mean change in HAM-A score from baseline to 12 weeks, mean change in HADS score from baseline to 12 weeks and the proportion of participants "much improved" or "very much improved" on CGI-I, proportion "much improved" or "very much improved" on PGI-I, and proportion of responders ( $> 50\%$  reduction from baseline or reduction to  $\leq 7$  in HAM-A) at 12 weeks. The secondary outcome regarding levodopa-induced dyskinesias will be the mean change in UDysRS score from baseline to 12 weeks. Similar analyses will be done for all outcomes at 2 weeks, 4 weeks, and 8 weeks. For participants lost to follow up, the

last observation carried forward will be used. We will also correlate mean change in the Parkinson Anxiety Scale scores with mean change in the CGI-I and PGI-I scores.

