## PROTOCOL SYNOPSIS

FULL STUDY TITLE	The Tolerability of Buspirone for Treatment of Anxiety in Parkinson's Disease
CLINICAL PHASE	Phase II
INVESTIGATORS/ STUDY GROUP	[name] (PI), [name] (Co-PI)
STUDY OBJECTIVE	The primary objective of this study is to determine the tolerability of buspirone for the treatment of anxiety in PD.
STUDY RATIONALE	Anxiety is highly prevalent in Parkinson's disease (PD) and negatively impacts quality of life yet it frequently remains untreated and there have been no clinical trials dedicated to evaluating the pharmacological treatment of anxiety in PD. Buspirone, which primarily acts as a 5HT1A receptor partial agonist, is effective for the treatment of generalized anxiety disorder in the general and elderly population. It is not known if it is effective for the treatment of anxiety in the PD population where there is a more heterogeneous phenomenology of anxiety. Buspirone also may diminish levodopa-induced dyskinesias. However, concerns have been raised about its potential to worsen motor function. A tolerability assessment is necessary prior to proceeding with a phase III efficacy trial.
STUDY SITES	University of Rochester
STUDY PERIOD	3 years
STUDY POPULATION AND NUMBER OF SUBJECTS	35 participants with idiopathic PD and clinically significant anxiety as defined by a score of $\geq 14$ on the self-rated Parkinson Anxiety Scale.
STUDY DESIGN	This is a single-center, placebo-controlled, double-blind design with participants randomized with a 4:1 allocation ratio to flexible dosage buspirone (maximum dosage 30 mg twice daily) or placebo for 12 weeks.

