SAMPLE SIZE CONSIDERATIONS	A sample size of 21 will provide 80% power to reject the null hypothesis of tolerability (observed intolerability rate of ≤20%) in favor of the alternative hypothesis of intolerability (observed intolerability rate of >20%) if the true intolerability rate is greater than 40%, using a binomial test and a one-tailed significance level of 10%. With the introduction of a placebo arm for blinding and relying on a 4:1 allocation ratio, the sample size increases to 27. The use of a futility design provides a higher probability of correctly failing to reject the null hypothesis of tolerability at the cost of a decreased chance of correctly rejecting the null hypothesis of tolerability. We are willing to accept a higher chance that we declare an intolerable drug tolerable as the expected intolerabilities (headache, nausea, drowsiness, dizziness, and worsening of PD motor function) are not expected to be severe, may be experienced by only a portion of subjects, and could be confirmed in larger studies.

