### 3. CHARACTERISTICS OF THE RESEARCH POPULATION

#### 3.1. Subject Characteristics

- a) **Number of Subjects:** 300. This number reflects the use of identified data during the screening process to identify potential participants. The total anticipated number of enrolled participants is 35, which includes screen failures.
- b) **Gender and Age of Subjects:** There will be no gender based enrollment restrictions. Participants will need to be at least 18 years of age. Based on the known demographics of PD, we anticipate that approximately 55-60% of the participants will be male and that the majority of participants will be over 50.
- c) **Racial and Ethnic Origin:** There will be no enrollment restrictions based upon race or ethnic origin. Based on the known demographics of PD and our patient population, we anticipate that the majority of the participants will be Caucasian.
- d) **Vulnerable Subjects:** PD is a disease that increases in prevalence with age and as such we expect a number of participants to be elderly. Participants will be able to withdraw from the study at any time.

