#### **4. SUBJECT IDENTIFICATION, RECRUITMENT AND CONSENT**

##### **4.1. Method Of Participant Identification And Recruitment**

We anticipate recruiting a total of 35 eligible participants at one site over a 24 month period. We will use multiple methods to identify potential participants.

(1) The primary investigator ([name]) and co-primary investigator ([name]) will use i2b2 (Informatics for Integrating Biology and the Bedside), a software for running clinical database queries, to query our electronic medical record (EMR) and identify patients with an ICD-9 diagnosis of 332.0 (parkinsonism) or ICD-10 diagnosis G20 (Parkinson's disease) *and* a diagnosis of an anxiety disorder who are seen by a URMC or URMC affiliated provider. For each identified patient, the primary care provider or neurologist in charge of their care will be contacted and permission to contact the identified patient will be requested.

(2) We will design and distribute informational flyers to local patient advocacy groups and affiliated and non-affiliated neurology, primary care, and psychiatry offices. Area providers will be sent informational letters and reference pocket cards. We will conduct informational presentations for area providers and promote the study at regional symposiums and other events. Additional efforts may be made to promote the study in the local media.

(3) The trial will be posted on appropriate clinical trial registries including Fox Trial Finder, clinicaltrials.gov and Research Match.

(4) We will reach out to local patient advocacy groups to increase awareness and engage potential participants.

A screening log will be maintained. The screening log will document how potential participants learned about the trial, where they were referred from, reasons for ineligibility, and reasons for nonparticipation of eligible participants. This information will be reviewed monthly to identify any problems and develop strategies to enhance recruitment.

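### The decision boundary of 7 failures has no denominator, the number to be randomised is unresolved (27 or 35), and the exact one-sided error exceeds the stated 10% (10.9% or 13.3% under 27)

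*Combined protocol and SAP*

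**What the plan says.** **The boundary.** Section 13.2 says that "if 7 or more participants fail to tolerate the study drug, the null hypothesis will be rejected". It gives no number out of which the 7 are counted and does not say that they are buspirone-arm participants. Non-completion for any cause counts as a failure (section 13.2), and withdrawn participants are not replaced (section 7.0).

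**The test.** Section 13.1 sets the acceptable limit at 20%, takes 40% as the alternative, and gives 80% power with 21 participants, "using a binomial test and a one-tailed significance level of 10% significance". Section 2.2 explains that sample size and analysis treat the trial as single-arm.

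**The number of participants.**

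- Section 13.1: "the desired sample size increases to 27". The sample-size row of the synopsis agrees: "relying on a 4:1 allocation ratio, the sample size increases to 27".
- Study-population row of the synopsis: "35 participants with idiopathic PD and clinically significant anxiety as defined by a score of" at least 14 on the Parkinson Anxiety Scale.
- Section 3.1: "The total anticipated number of enrolled participants is 35, which includes screen failures".
- Section 4.1: "We anticipate recruiting a total of 35 eligible participants at one site over a 24 month period".

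Section 8.3 gives the 4:1 ratio but no arm sizes and no block size.

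**The concern.** A fixed count has an error rate only once the denominator is fixed. Here the denominator must be inferred, and the documents point to more than one value for it.

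The direction of the error matters. The null hypothesis is that buspirone is tolerable, so the one-tailed 10% is the chance of wrongly declaring it intolerable. Section 13.1 says this is the mistake to be guarded against: "We are more concerned about declaring a truly tolerable drug intolerable and not moving forward with larger studies". If the boundary stays at 7 while the arm grows, this is the error that rises. No other formal test in the plan offsets it.

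**Working it through.** **Inputs.** Null rate 0.20, alternative 0.40, one-tailed level 0.10, 21 on buspirone, 80% power, total 27 (section 13.1); boundary of 7 (section 13.2); 4:1 allocation (section 8.3); 35 participants (synopsis, sections 3.1 and 4.1).

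**Formula.** With X failures among n on buspirone and true failure rate p,

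P(X ≥ c) = 1 − Σ (k = 0 to c − 1) C(n, k) p^k (1 − p)^(n − k).

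The error is this tail at p = 0.20, and the power is the tail at p = 0.40.

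**Step 1: reproduce the plan's own figures (n = 21, c = 7).**

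- Power: 1 − 0.2002 = 0.7998, which is the stated 80%.
- Error: 1 − 0.8915 = 0.1085, which is 10.9%, not 10%.
- Total: 21 / 0.8 = 26.25, rounded up to 27, as stated.

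So 7 of 21 is very probably the intended rule, and only the error fails to reproduce.

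**Step 2: arm sizes that the documents imply.**

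- 27 × 0.8 = 21.6, so 21 or 22 on buspirone.
- 35 × 0.8 = 28, if all 35 were randomised.
- 35 agrees with 27 if 35 − 27 = 8 fail screening (8/35 = 22.9%). This fits section 3.1, which counts screen failures within the 35. It does not fit section 4.1, which calls all 35 eligible.

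**Step 3: keep the boundary at 7 and vary the arm.**

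| On buspirone | Error at 20% | Power at 40% |
|---|---|---|
| 20 | 8.7% | 75.0% |
| 21 | 10.9% | 80.0% |
| 22 | 13.3% | 84.2% |
| 28 (only if 35 are randomised) | 32.2% | 96.9% |

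**Step 4: smallest boundary with exact error of at most 10%.** This is 7 for arms of 17 to 20, 8 for 21 to 24, and 9 for 25 to 28.

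| On buspirone | Boundary | Error at 20% | Power at 40% |
|---|---|---|---|
| 21 | 8 | 4.3% | 65.0% |
| 22 | 8 | 5.6% | 71.0% |
| 24 | 8 | 8.9% | 80.8% |
| 28 | 9 | 9.0% | 85.2% |

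The smallest arm that meets both 10% error and 80% power exactly is 24, which is 24 / 0.8 = 30 in total at 4:1.

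**Step 5: where the 7 may come from.** A normal-approximation test at n = 21 uses z = (X/21 − 0.20) / √(0.16/21). Seven failures give z = 1.53 and six give z = 0.98, against a critical value of 1.28. The cut-off of 7 is therefore what a large-sample test at 10% would yield.

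**The case against.** The intended rule can be recovered. Section 2.2 calls the analysis single-arm, section 13.1 gives one test size (21), and 7 of 21 returns the stated power. Section 13.1 asks for a binomial test but not explicitly an exact one, and Step 5 shows that 7 is the nominal 10% boundary under a normal approximation. The excess at 21 is then 0.85 percentage points, which is small in a phase II trial. The figure of 22 appears nowhere in the documents. Section 3.1 defines the 35 as including screen failures, so the word eligible in section 4.1 may be loose wording, and no section says that 35 will be randomised.

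Much of this stands. At 21 alone the gap is modest, and the 32.2% is conditional on a reading that the plan never states outright. But the normal approximation explains only why 7 was chosen. It does not change the error that the rule attains, which is a property of the binomial distribution. Section 13.1 derives 27 from 21, but 27 at 4:1 does not return 21 exactly, and nothing in section 8.3 fixes the split. Sections 3.1 and 4.1 also conflict as written, because a screen failure is not an eligible participant. A trial's single decision rule should not rest on choosing between them.

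**Conclusion.** The concern holds. The boundary in section 13.2 is not tied to a denominator, the number to be randomised is not settled, and the stated one-tailed 10% is exceeded at every arm size the documents imply: 10.9% at 21, 13.3% at 22 and, only if all 35 are randomised, 32.2% at 28. Under an exact test, 21 participants, 10% error and 80% power cannot all be true together.

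This assumes that the test applies to buspirone participants only and that everyone randomised to buspirone is in the denominator. The second assumption follows from counting every non-completion as a failure and not replacing withdrawals. The point should be fixed before the analysis; at the likely arm of 21 the numerical excess is small, and the greater weakness is a count that does not adjust to the arm size.

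**What to change.** 1. Reconcile the synopsis and sections 3.1, 4.1 and 13.1 to one number to be randomised, and state separately how many are to be screened.
2. In section 13.2, say that the count refers to participants randomised to buspirone, and define the boundary from the number actually randomised to that arm, as the smallest count with exact binomial probability of at most 0.10 at a true rate of 20%. The second table above gives examples, such as 9 or more of 28.
3. If a total of 27 stands and 7 is kept to preserve 80% power, restate the one-sided error as 10.9% (21 on buspirone) or 13.3% (22).
4. Minor: state the hypotheses in the synopsis and section 13.1 in terms of the true failure rate, not the observed one. As written they conflict with the rule, because 6 of 21 is an observed 28.6%, above 20%, yet does not lead to rejection.

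**Cost.** Items 1 to 4 change wording only and need no extra patients. Keeping 7 means reporting a less favourable error. Holding 10% with a boundary of 8 lowers power from the stated 80% to 65.0% at 21 or 71.0% at 22. Meeting both targets exactly would take 24 on buspirone and 30 in total, three more than 27.
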